##### Study Visits and Assessments

- (1) For subjects aged under 14 years that are still participating in the study but not currently receiving palovarotene treatment as per the global partial clinical hold or for any other reason, they will complete Part C EOT/EOS and be invited to participate in Part D and undergo assessments outlined in Table 4.**

- (2) **For subjects aged 14 years and older who are being considered for re-starting palovarotene treatment but have NOT yet re-started**, the following minimum assessments are to be done via remote monitoring (video conference/phone calls) by the Investigator (or delegated study staff):
- (a) Non-flare-up-based visits every 3-6 months (per protocol): assess for childbearing status (females only) and pregnancy prevention measures, CAJIS, ConMeds, adverse events, review subject diary, PROMIS Global Health Scale\*, FOP-PFQ\* (\*assessments that can occur remotely but not required as these are not essential to ensure subjects' safety).
  - (b) For females of childbearing status: if pregnancy testing did not continue monthly per protocol post the study medication interruption then at a minimum a self-administered urine pregnancy test is to be done within 4 weeks before re-starting palovarotene treatment.
  - (c) All subjects should have laboratory assessments (hematology, biochemistry, urinalysis) within 4 weeks before re-starting palovarotene treatment.
  - (d) All subjects who were skeletally immature at the last assessment will have a hand-wrist and knee radiographs within 12 weeks before re-starting palovarotene treatment. For on-treatment subjects who have not reached at least 90% skeletal maturity radiograph assessments should continue per protocol either on site or remotely.

Site staff will also assess the subject's ability to restart remotely.

- (3) **For subjects 14 years and over that plan to reinitiate dosing, once dosing is reinitiated following the required approvals for restart (Ethics Committee and Competent Authority)**, the following minimum assessments that cannot be performed via remote monitoring must be performed either at the clinical site, at the subject's home (by Symphony nursing) or at a local medical facility in order for the Investigator to adequately monitor the safety of subjects:
- (a) Via remote monitoring (telephone or video conferencing) by Investigator (or delegated study staff):
    - i. Non-flare-up-based visits (per protocol schedule every 3 and/or 6 months): C-SSRS, assess for childbearing status (females only) and pregnancy prevention measures, CAJIS, ConMeds, adverse events, PROMIS Global Health Scale\*, FOP PFQ\* (\*assessments that can occur remotely but are not required as these are not essential to ensure subjects' safety), study drug dispensing
    - ii. Flare up visits (per protocol schedule): C-SSRS, ConMeds, adverse events, study drug dispensing
  - (b) Via home visit by Symphony nursing/local assessment
    - i. Non-flare-up-based visits per protocol schedule (every 3 and/or every 6 months): body weight, vital signs, hematology, biochemistry, urinalysis, self-administered pregnancy test (monthly), ConMeds, adverse events, review subject diary

- ii. Flare up visits (per protocol schedule): vital signs, body weight, hematology, biochemistry, urinalysis, self-administered pregnancy testing, ConMeds, adverse events, review subject diary
- (4) **Based on the known safety profile of palovarotene to date in FOP patients, the following assessments can be postponed as determined by the Sponsor and individual site Investigators, as they do not constitute assessments where a safety concern has been raised.** The below assessments were also deemed acceptable to postpone by the DMC chair.
- (a) To date low dose whole-body CT has not indicated a safety concern of avascular necrosis of the hip. Any concerns for avascular necrosis of the hip based on clinical assessment should be followed up;
  - (b) For subjects who have reached at least 90% skeletal maturity radiograph assessments may be postponed given the low risk of early growth plate closure as well as growth plate abnormalities;
  - (c) Linear height and knee height (Subjects 14 years and older are at or near adult height indicated by skeletal maturity of at least 90%);
  - (d) ECG (FOP patients can have ECG abnormalities, ECG changes noted in subjects on Palovarotene were similar to those seen in the untreated subjects in the Natural History Study. Clinical concerns of abnormal ECG findings should continue to be followed);
  - (e) Hearing evaluation (As a class, retinoids can cause abnormal hearing. Evaluation should be performed if there is clinical concern);
  - (f) Physical exam (Palovarotene has been shown to cause retinoid skin reactions which can be assessed remotely).

Individual subjects may require assessments if there is a clinical concern as identified by the Investigator. Protocol deviations that have an impact on subject safety should be notified immediately to CRO/Sponsor as it may necessitate an urgent safety measure notification to competent authorities and ethics committees in some countries.

(5) **End of Treatment/End of Study Assessments:**

- (a) The following assessments should be performed via remote monitoring (telephone or video conferencing) by Investigator (or delegated study staff):
    - i. C-SSRS, assess for childbearing status (females only) and pregnancy prevention measures, CAJIS, Con-Meds, adverse events, PROMIS Global Health Scale, FOP PFQ
  - (b) The following assessments should be performed at the subject's home (by Symphony nursing) or at a local medical facility: Body weight, vital signs, hematology, biochemistry, urinalysis, pregnancy test (monthly), ConMeds, adverse events, review subject diary
- (6) **Once on-site visits resume, the following assessments should be performed on site as well as any assessment that was not obtained via remote monitoring or Symphony nurse:**
- (a) X-rays, Whole-Body CT, Linear and Knee Height, Physical Exam, ECG.

- (7) **Informed Consent/Subject Communication:** In consultation with their site IRB/EC, Investigators are required to inform subjects of the temporary changes (during the COVID-19 global pandemic) to the study conduct and monitoring plans that could impact them and their willingness to continue participation in the trial. The method of communication to subjects (e.g., email, phone call, information letter) and documentation of subject/caregiver acknowledgement is to be performed and documented in accordance with local regulations/EC requests and guidance. All contacts with subjects must be filed in the source records.

A risk mitigation assessment will be performed for each subject at the site in order to determine how their participation may be impacted. Sites must ensure that appropriate measures are taken to ensure the safety of FOP subjects in light of the ongoing COVID-19 pandemic, taking into consideration local Ethics Committee and Competent Authority guidance, as well as the ability of individual Investigators and sites to adequately monitor subject safety.

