The primary efficacy endpoint implemented for Amendment 3 and subsequent amendments is the annualized change in new HO volume (as assessed by low-dose WBCT scan, excluding head). The annualized change will be compared to data collected from a natural history study using a weighted linear mixed effects model with baseline HO volume divided by age as the only covariate and weights used to account for the different lengths of observed subject follow-up. A subject-specific random effect will be included to account for within-subject correlation.

**Table 1 Schedule of Assessments During Non-Flare-up-based Treatment (Subjects from Amendment 1 Continuing Non-Flare-up-based Treatment)**

Assessment/Procedure	Amendment 3 Consent/Assent  (Remote Visit)	Every Month Remote Visit  (±1 week)	Every 3 Months Remote Visit  (±2 weeks)	Months 6, 18, 30, 42, 54, 66 Remote Visit  (±1 month)	Months 12, 24, 36, 48, 60 72/EOT/EOS  Site Visit (±1 month)
Informed consent/assent 	X				
Inclusion/exclusion	X				
Knee and hand/wrist radiographs 			X 	X	X
Linear growth assessment (stadiometry, knee height; subjects <18 years of age) 				X	X
Physical examination					X
Body weight			X	X	X
Electrocardiogram					X
Study drug dispensing	As needed from Non-flare-up Day 1 through Month 72				
Study drug treatment	Continuous from Non-flare-up Day 1 through Month 72 				
Dispense/review subject diary	Dispense diary as needed and review at every subject contact				
Vital signs			X	X	X
C-SSRS (age-appropriate)			X	X	X
Hematology 				X	X
Biochemistry (includes lipids, serum pregnancy test) 				X	X
Urinalysis 				X	X
Pregnancy test 		X			
FOP-PFQ 				X	X
PROMIS Global Health Scale 				X	X
CAJIS				X 	X
Low-dose WBCT scan, excluding head 					X
Prior/concomitant medications	At every subject contact				
Adverse events	At every subject contact				
Pharmacokinetic blood sample 			Month 3 only		
Telephone contact 			X		

- 1 Visits can be combined with flare-up visits when appropriate.

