### 7.2.7 *Pregnancy Testing*

For females of child bearing potential receiving palovarotene, a blood or urine pregnancy test (with sensitivity of at least 50 mIU/mL) will be conducted monthly in Parts A, B and C. If the Screening test is positive, the subject will not be eligible for study participation. Any positive pregnancy test during study participation will result in immediate discontinuation of study drug. If a subject becomes pregnant during the study, she will be followed throughout her pregnancy and the health status of the baby will be verified.

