#### **7.7 Temporary Measures (Procedures Related to COVID-19 Pandemic)**

##### **Procedures related to COVID-19 pandemic**

Temporary measures put in place for the conduct of Study PVO-1A-204 during the COVID-19 pandemic and until such time as the situation resolves, at which point the protocol assessments will return to those specified. Investigators will determine the feasibility of dosing on a subject-by-subject basis, depending on the ability to conduct safety monitoring and providing subjects an adequate supply of study drug, in accordance with local requirements. These recommendations will remain in place for as long as the COVID-19 pandemic warnings are in effect in territories participating in the trial. The timing of when the pandemic is declared over may vary on a country-by-country basis as well as between sites in the same country, and as such the temporary measures may remain in place for differing periods of time per country/site.

The study visits and assessments to be conducted during this period are listed below:

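### PVO-1A-204 schedules a check of childbearing status and contraception only in its temporary COVID-19 measures; its standing schedule lacks the 3-monthly recheck that PVO-1A-202 has

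*Protocol*

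**What the plan says.** The document holds two protocols, PVO-1A-202 (Amendment 8) and its French counterpart PVO-1A-204 (Amendment 6).

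PVO-1A-204 mentions the check three times, all in Section 7.7 (Temporary Measures):

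- Item 2a, subjects aged 14 or over who have not yet restarted: "Non-flare-up-based visits every 3-6 months (per protocol): assess for childbearing status (females only) and pregnancy prevention measures". Item 2 introduces its list with "the following minimum assessments are to be done via remote monitoring".
- Item 3a, subjects who have restarted: "Non-flare-up-based visits (per protocol schedule every 3 and/or 6 months): C-SSRS, assess for childbearing status (females only) and pregnancy prevention measures".
- Item 5a, end of treatment or study: "assess for childbearing status (females only) and pregnancy prevention measures".

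Section 7.7 applies "until such time as the situation resolves, at which point the protocol assessments will return to those specified".

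The standing parts of PVO-1A-204 cover pregnancy testing only. Section 7.2.7 opens "For females of child bearing potential receiving palovarotene, a blood or urine pregnancy test", makes the test monthly, and goes on to what follows a positive result. Table 1 ("Subjects from Amendment 1 Continuing Non-Flare-up-based Treatment") includes a serum test in its row "Biochemistry (includes lipids, serum pregnancy test"), but neither Table 1 nor Table 2 has a row for childbearing status or contraception.

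PVO-1A-202 has such a row in both its Table 1 and its Table 2, marked at the 3-monthly, 6-monthly and annual visits. Its Section 7.2.7 adds a sentence requiring the reassessment every 3 months, covering status in females and prevention measures in both sexes.

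**The concern.** Section 7.7 is the pared-down regime. It keeps the contraception check as part of minimum safety monitoring. It does not mark the check as non-essential, as it does the two questionnaires in items 2a and 3a, and item 4 does not list it as postponable. When the temporary measures lapse, the protocol returns to a schedule without the check, so the full regime protects less than the emergency one.

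Section 7.3.10 says pregnancy on any amount of drug, even briefly, carries an extremely high risk of severe birth defects. Three things are then left without a scheduled question:

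- **Contraception in females of childbearing potential.** A pregnancy test finds an exposure that has already started; a question about contraception comes before it.
- **Contraception in males.** Section 5.6.2 places the same duty on them during treatment and for 1 month after, and no pregnancy test covers them.
- **Childbearing status itself.** The monthly tests and monthly visits are directed to females of childbearing potential, and the standing schedule never explicitly re-asks that status over treatment lasting up to 48 or 72 months.

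**Working it through.** **Comparing the standing provisions**

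| Place | PVO-1A-202 | PVO-1A-204 |
|---|---|---|
| Table 1 | Row present | Absent; C-SSRS is followed directly by hematology |
| Table 2 | Row present | Absent; same sequence |
| Section 7.2.7 | 3-monthly sentence present | Absent |
| Table 3 (flare-up) | Absent | Absent |

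PVO-1A-202 has the check in three of the three relevant places and PVO-1A-204 in none. The footnotes to PVO-1A-204 Tables 1 and 2 do not supply it. Table 3 lacks the row in both protocols, so the difference is confined to the other three places. In Section 7.7 the words about protocol timing are taken to describe when visits occur; the finding does not depend on reading them as a claim that the check is already in the tables.

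At one recheck every 3 months, the PVO-1A-202 schedule implies 72/3 = 24 over 72 months or 48/3 = 16 over 48 months. The PVO-1A-204 standing schedule implies 0.

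**What still stands in PVO-1A-204**

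- The contraception agreement at entry and during treatment (5.4.1, 5.6.2).
- Monthly pregnancy tests for females of childbearing potential (7.2.7), and the serum test within Table 1 biochemistry.
- Tests at the start of each flare-up cycle and every 4 weeks after (Table 3, footnote 6).
- Concomitant medication review at every visit (7.2.9).
- Physical examination at least annually (7.2.2).

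None of these is a scheduled check of contraception or an explicit recheck of status.

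**How many contacts could be affected**

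Inputs: Amendment 3 dated 22 March 2018 (Synopsis); Amendment 6 finalized 18 December 2020 (Amendment Summary); up to 48 additional months of treatment; about nine subjects (Synopsis). Assumption: each subject's 48 months began between 22 March 2018 and 12 months later.

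- Earliest start: 22 March 2018 + 48 months = 22 March 2022. From 18 December 2020 that leaves 15 whole months, and 15/3 = 5 contacts.
- Latest start: 22 March 2019 + 48 months = 22 March 2023. That leaves 27 whole months, and 27/3 = 9 contacts.
- Contacts while Section 7.7 is in force are covered. It has no stated end date, so the number covered runs from none to all, leaving 0 to 9 uncovered per subject.
- Upper bound over the cohort: 9 subjects × 9 contacts = 81. Lower bound: 0.

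The upper bound treats all nine as still on drug. Fewer will be, because children under 14 are not restarted. The protocol gives no count by sex or of subjects still dosed.

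**The case against.** The strongest reply is that nothing in PVO-1A-204 is contradictory. It is a separate protocol that differs from its sister in other ways (extra ECGs, dosing diaries for compliance, weight-based flare-up dosing to age 18), and the statement that the two correspond does not promise identical schedules. That is fair: a difference from PVO-1A-202 is not in itself an error. The point nevertheless survives on PVO-1A-204 alone, because its temporary minimum contains a safety check that its full schedule lacks, and no reason is given.

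The second reply is that other safeguards carry the load. Section 5.6.2 is a continuing duty, Section 7.3.10 bars use by females who may become pregnant, Section 9.1.9 requires reporting of a partner's pregnancy, and running monthly tests in the right subjects implies that the site knows their current status. Any female still dosed is at least 14, which narrows the risk of a girl passing into childbearing potential unnoticed. Medication review would show a change in hormonal contraception. All of this holds, and it limits the consequence. But no scheduled visit verifies the duty in Section 5.6.2, partner reporting comes after the event, an implied duty need not be documented, and medication review does not reach barrier methods or abstinence.

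The third reply is scale: the count could be nil if Section 7.7 outlasts treatment in this closed cohort. That also stands, and it bears on urgency more than on whether to make the edit.

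**Conclusion.** The concern holds. PVO-1A-204's standing schedule contains no recheck of childbearing status or contraception, while its own temporary minimum and the sister protocol both do. Following the protocol as written would reduce pregnancy-prevention monitoring of a teratogen when normal conduct resumes.

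The consequence is limited: about nine subjects at most, one site, and 0 to 9 uncovered contacts per subject (0 to 81 in all). That range rests on the assumed 12-month spread of start dates and on the unknown end of Section 7.7. No endpoint, estimate or test is affected. This should be corrected because the possible harm is severe and irreversible and the remedy is very cheap; it does not threaten the trial's conclusions.

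**What to change.** In PVO-1A-204, add to Tables 1 and 2 the row that PVO-1A-202 already uses for reassessing childbearing status (females) and pregnancy prevention measures (females and males), marked at the 3-monthly, 6-monthly and annual visits. Add the matching 3-monthly sentence from PVO-1A-202 Section 7.2.7 to PVO-1A-204 Section 7.2.7.

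The cost is one row in each of two tables and one sentence in a single-site protocol, plus a brief question at contacts that already take place. No new visit, sample or test is needed.

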## 8 STATISTICAL AND ANALYTICAL PLANS

This study is intended to assess whether a non-flare-up based dosing regimen, combined with higher doses during times of flare-ups, will result in a lower incidence of new HO formation. As this is an open-label study with no comparator arm, use of subject data from Study PVO-1A-001 (Natural History Study [NHS]) will form the basis for a control arm. Additional analysis of the flare-up-based treatment regimen will be described in the Statistical Analysis Plan (SAP).

A summary of the general methods and strategies for analysis is provided in the sections below. A more comprehensive SAP will be written that will describe the manner in which the analysis will be performed.

References to Parts B/C/D are to PVO-1A-202 Parts B/C/D which corresponds to PVO-1A-204, ongoing in France.

### 8.1 General Methods

For purposes of assessing the efficacy of the non-flare-up based dosing regimen, low-dose WBCT imaging data obtained under the original protocol and all amendments will be combined.

### 8.2 Sample Size

The new HO volume data as assessed by low dose WBCT scan, excluding head, from the original protocol and all amendments will be combined. The sample size was fixed by the number of subjects enrolled in the original protocol and Amendment 1 and was not based on power calculations.

### 8.3 Study Populations

The following populations will be analyzed under Amendment 3 (and all subsequent amendments):

- The Full Analysis Set (FAS) includes all enrolled subjects having a baseline
- HO volume measurement and at least one post-baseline HO volume measurement. For efficacy comparisons to the NHS, the FAS will also include subjects enrolled in the NHS with available baseline and at least one post-baseline HO volume measurements.

- The Per-Protocol Set (PPS) is a subset of the FAS including subjects with no major protocol deviations that are expected to interfere with assessments of the primary endpoint, and with at least 80% compliance to the study drug regimen. For efficacy comparisons to the NHS, the PPS will also include subjects in the NHS with available baseline and at least one post-baseline HO volume measurements and with no major protocol deviations that are expected to interfere with assessments of the primary endpoint.
- The Safety Analysis Set (SAS) includes all enrolled subjects receiving at least one dose of palovarotene during Amendment 2. For safety comparisons to the NHS, the SAS will also include subjects enrolled in the NHS with available post-baseline follow-up.
- The Pharmacokinetic Analysis Set (PAS) is a subset of the SAS including subjects with evaluable pharmacokinetics data.

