## Palovarotene Phase 2 Interventional Studies

The Phase 2 interventional studies for which subjects with FOP have received treatment include:

- Study PVO-1A-201 provided a preliminary assessment of palovarotene efficacy across two different dosing regimens following 6 weeks of treatment for a flare-up relative to placebo (ie, flare-up only regimen). Forty subjects were randomized (3:3:2) within 1 week of a flare-up to receive either 10 mg palovarotene daily for 2 weeks followed by 5 mg daily for 4 weeks (10/5 mg); 5 mg palovarotene for 2 weeks followed by 2.5 mg for 4 weeks (5/2.5 mg); or placebo for 6 weeks. After the 6-week treatment period, subjects began a 6-week follow-up period during which no study drug was administered.
- Study PVO-1A-202/Part A, an open-label extension of Study PVO-1A-201, evaluated the long-term safety and efficacy of prior palovarotene treatment after an additional 12 months of follow-up. Open-label palovarotene was administered to all subjects, including any randomized to placebo during Study PVO-1A-201, experiencing additional eligible flare-ups (ie, flare-up only regimens). Subjects were treated with high dose palovarotene (10 mg palovarotene for 2 weeks followed by 5 mg for 4 weeks) regimen for 6 weeks, followed by a 6-week period in which no study drug was administered.
- Study PVO-1A-202/Part B (corresponds to Study PVO-1A-204 in France) included chronic daily doses (5 mg) of palovarotene in subjects with at least 90% skeletal maturity. During a flare-up, all subjects received higher dose/longer duration treatment with palovarotene (20 mg for 4 weeks followed by 10 mg for 8 weeks). This “chronic/flare-up” regimen is the dosing regimen employed in the current study, PVO-1A-202/Part C, that will include chronic or non-flare-up dosing for skeletally mature as well as skeletally immature subjects. This corresponds to Study PVO-1A-204 Amendment 3 in France.
- Study PVO-1A-202/Part C (corresponds to Study PVO-1A-204 in France, ongoing) extends the chronic/flare-up palovarotene regimen to all subjects, including skeletally immature children. Part D was added for skeletally immature subjects who stopped taking study drug for any reason before completion of Part A/B/C. Part D includes yearly visits for up to a 2-year follow-up period following last dose. No dosing is to occur during Part D.

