### **Part D:**

Annual post last dose of study treatment assessments for up to 2 years will be obtained in subjects who were skeletally immature at the time of study treatment discontinuation in order to obtain longer-term safety data. No new subjects will be enrolled into Part D. Subjects who were enrolled in Parts A, B or C who have discontinued the study and were skeletally immature at their last assessment will be invited back to participate in the off-treatment Part D safety follow-up. These subjects will follow all procedures and undergo all assessments as specified in the Schedule of Assessments in [Table 4](#).

Assessments will include knee and hand/wrist radiographs, linear and knee height growth assessments, physical examination, body weight, vital signs, low-dose WBCT scan (excluding head), prior/concomitant medications, and adverse events.

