## 8.3 Study Populations

The following populations will be analyzed under Amendment 4 and subsequent amendments:

- The Full Analysis Set (FAS) includes all enrolled subjects having a baseline HO volume measurement and at least one post-baseline HO volume measurement in the PVO-1A-202 study. For efficacy comparisons to the NHS, the FAS will also include subjects enrolled in the NHS with available baseline and at least one post-baseline HO volume measurements.
- The Per-Protocol Set (PPS) is a subset of the FAS including subjects with no major protocol deviations that are expected to interfere with assessments of the primary endpoint, and with at least 80% compliance to the study drug regimen. For efficacy comparisons to the NHS, the PPS will also include subjects in the NHS with available baseline and at least one post-baseline HO volume measurements and with no major protocol deviations that are expected to interfere with assessments of the primary endpoint.
- The Safety Analysis Set (SAS) includes all enrolled subjects receiving at least one dose of palovarotene in the PVO-1A-202 (after Amendment 3). For safety comparisons to the NHS, the SAS will also include subjects enrolled in the NHS with available post-baseline follow-up.
- The Pharmacokinetic Analysis Set (PAS) is a subset of the SAS including subjects with evaluable pharmacokinetics data.

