### **8.8.3 Clinical Laboratory Findings**

Change in clinical laboratory findings, vital signs, and other continuous safety parameters will be assessed descriptively, with pre-treatment, on-treatment, and change from pre-treatment values calculated. For purposes of this analysis, pre-treatment will be the last values prior to initiation of non-flare-up-based dosing.

Group-mean plots (mean and standard error) over time will be provided.

The number and percentage of subjects with potentially clinically significant (PCS) values will be summarized. A focus will be on new-onset PCS values, ie, subjects with pre-existing PCS values at pre-treatment will not be considered to have new-onset values on-treatment.

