AE = adverse event, CAJIS = Cumulative Analogue Joint Involvement Scale for FOP, C-SSRS = Columbia Suicide Severity Rating Scale, EOS = end of study, EOT = end of treatment; FOP-PFQ = Fibrodysplasia Ossificans Progressiva physical function questionnaire, PROMIS = Patient Reported Outcomes Measurement Information System, WBCT = whole body computed tomography.

**Table 2 Schedule of Assessments During Non-Flare-up-based Treatment  
(Subjects from Amendment 1 Starting Non-Flare-up-based Treatment)**

Assessment/ Procedure	Amendment 3 Screening/ Non-Flare-Up Day 1  / Site Visit (-1 month)	Non-Flare-Up Day 7 (±3 days)	Every Month Remote Visit  (±1 week)	Every 3 Months Remote Visit  (±2 weeks)	Months 18, 30 42 Remote Visit  (±1 month)	Months 6, 12, 24, 36, 48/EOT/ EOS  Site Visit (±1 month)
Informed consent/assent 	X					
Inclusion/exclusion	X					
Knee and hand/wrist radiographs for assessment of epiphyseal growth plate 	X			X 	X	X
Linear and knee height growth assessments (<18 years of age) 	X				X	X
Physical examination	X					X
Body weight	X			X	X	X
Electrocardiogram	X	X 				X
Study drug dispensing	As needed from Non-flare-up Day 1 through Month 48					
Study drug treatment	Continuous from Non-flare-up Day 1 through Month 48 					
Dispense/review subject diary	Dispense diary as needed and review at every subject contact					
Vital signs	X			X	X	X
C-SSRS (age-appropriate)	X			X	X	X
Hematology 	X				X	X
Biochemistry (includes lipids) 	X				X	X
Urinalysis	X				X	X
Pregnancy test 			X			
FOP-PFQ 	X				X	X
PROMIS Global Health Scale 	X				X	X
CAJIS	X				X 	X
Low-dose WBCT scan, excluding head	X					X 
Prior/concomitant medications	At every subject contact					
Adverse events	At every subject contact					
Pharmacokinetic blood sample 				Month 3 only		
Telephone contact 				X		

- 1 A visit will be scheduled as soon as possible after Amendment 3 is approved at the clinical site and non-flare-up-based treatment will be started during that visit (Non-flare-up Day 1). Visits can be combined with flare-up visits when appropriate.

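### Both safety analysis sets depend on an amendment instead of on any palovarotene dose: the PVO-1A-204 definition contradicts its own section, and the PVO-1A-202 one leaves out Part A-only subjects

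*Protocol*

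**What the plan says.** **PVO-1A-204, Section 8.3.** The section opens with "The following populations will be analyzed under Amendment 3 (and all subsequent amendments"). The SAS is then limited to enrolled subjects "receiving at least one dose of palovarotene during Amendment 2". The Pharmacokinetic Analysis Set (PAS) is a subset of the SAS. The Full Analysis Set carries no amendment condition, and Sections 8.1 and 8.2 pool efficacy imaging over the first protocol version and every amendment.

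**PVO-1A-204, Table 2, footnote 1.** For subjects starting daily (non-flare-up) treatment: "A visit will be scheduled as soon as possible after Amendment 3 is approved at the clinical site and non-flare-up-based treatment will be started". Section 3.1 likewise places their Non-flare-up Day 1 under Amendment 3.

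**PVO-1A-202, Section 8.3.** The SAS is enrolled subjects "receiving at least one dose of palovarotene in the PVO-1A-202 (after Amendment 3"). Section 3.1 defines Part A as everything before Amendment 3. Under Part D it invites back "Subjects who were enrolled in Parts A, B or C who have discontinued the study" if they were skeletally immature at their last assessment.

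**Both protocols, Section 8.8.3.** For laboratory values, vital signs and other continuous safety parameters, "pre-treatment will be the last values prior to initiation of non-flare-up-based dosing" (quoted from PVO-1A-202; the PVO-1A-204 rule is the same). For potentially clinically significant (PCS) values, "subjects with pre-existing PCS values at pre-treatment will not be considered to have new-onset values on-treatment". On Part B, Section 1.1.3.2 says: "During a flare-up, all subjects received higher dose/longer duration treatment with palovarotene".

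**The concern.** A safety set should contain everyone who took the drug. When membership depends on the protocol version in force on the day of dosing, exposed subjects can fall outside every safety table for a reason unrelated to exposure. In PVO-1A-204 a subject can count for efficacy and not for safety, because only the safety set carries the amendment condition. In PVO-1A-202, Part D collects radiographs, CT scans and growth measurements from a group that may include people outside the SAS. Safety is part of the primary objective in both protocols, and Part D exists only for safety.

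The baseline raises a related, smaller question. If the value called pre-treatment was taken after courses of the drug, it is not drug-free.

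**Working it through.** No figure in the plan can be reproduced here, since Section 8.2 of both protocols says sample size was not based on power. The check is a comparison of passages plus simple arithmetic on set size.

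**1. Who meets the PVO-1A-204 condition?**
- Dosed under the first protocol version or Amendment 1 only: exposed, not in the SAS.
- Dosed during Amendment 2, whatever came before or after: in the SAS.
- First dosed under Amendment 3 or later: exposed, not in the SAS, although Section 8.3 says the populations are for that period.

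The document does not settle how many subjects are in each row. Section 3.2 says daily dosing reached the paediatric cohort under Amendment 2, whereas Section 3.1 and Table 2 say Amendment 3. The text as supplied gives no date for Amendment 2.

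**2. Size in PVO-1A-204.** Enrolment is up to 7 roll-over subjects plus up to 2 new adults: 7 + 2 = 9, matching the stated total. Let k be the number of exposed subjects omitted. The documents give no k, so the values below are assumptions. The share lost is k/9. With no events observed, the one-sided 95% upper bound on an event rate is 1 − 0.05^(1/n), where n = 9 − k.

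| k (assumed) | n | Share lost | Upper bound, 0 events |
|---|---|---|---|
| 0 | 9 | 0% | 28.3% |
| 1 | 8 | 11.1% | 31.2% |
| 2 | 7 | 22.2% | 34.8% |
| 3 | 6 | 33.3% | 39.3% |
| 4 | 5 | 44.4% | 45.1% |

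As an illustration, if the one omitted subject had the only event of a given type, the table would show 0/8 = 0% in place of 1/9 = 11.1%.

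**3. Who is missing in PVO-1A-202?** Sections 8.1 and 8.2 attach the same after-Amendment-3 label to Part B, so the SAS covers Part B onward. The 20/10 mg flare-up regimen was used in Part B; Part A used 10/5 mg. Children treated for flare-ups in Part B are therefore in the SAS. Subjects dosed in Part A and never again are not. Table 4, footnote 1 schedules Part D visits for people who finished in Part A.

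**4. Is the Section 8.8.3 baseline drug-free?** In Part B, daily dosing was for subjects with at least 90% skeletal maturity, while flare-up dosing was for all. A skeletally immature child could therefore have one or more flare-up courses (12 weeks each, extended if the flare-up persisted) before the pre-treatment value. Earlier exposure is also likely among roll-overs: Study 201 allocated 3:3:2 with two palovarotene arms, so (3 + 3)/8 = 75%, or 30 of 40. Applied to up to 7 roll-overs in PVO-1A-204, 7 × 0.75 = 5.25, about 5, assuming they reflect the overall allocation. Subjects who cannot take daily treatment but are treated for flare-ups (Section 6.4 of PVO-1A-204; Section 3.1 of PVO-1A-202) have no pre-treatment value under this rule. Extent of exposure (Section 8.6), by contrast, runs from the first dose.

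**The case against.** The strongest reply is that the PVO-1A-204 wording is a stale version label and not a policy. The same drift appears elsewhere in that protocol: the synopsis names Amendments 1 and 2 for the primary endpoint where Section 4.1 names 1 and 3, and Section 7.2.2 refers to Amendment 2 screening where Section 7.2.3 refers to Amendment 3. That is probably right, but it explains the error without removing it. The sentence is current text and an analyst would have to apply it or override it.

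A reader might also infer that the analysis leaves out the flare-up regimen and so conceals premature growth plate closure. The documents do not support this. In PVO-1A-202, Part B flare-up exposure stays in the SAS. In both protocols, clinically significant radiographic findings are recorded as adverse events (Section 7.3.2), and adverse event incidence (Section 8.8.1) does not use the Section 8.8.3 baseline. Closures among SAS members are counted.

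Nor does the baseline rule absorb every laboratory effect of earlier courses. Subjects starting daily treatment in Part C, or under Amendment 3 in PVO-1A-204, are excluded if amylase or lipase exceeds 2 times the upper limit of normal (ULN), AST or ALT exceeds 2.5 times ULN, or fasting triglycerides exceed 400 mg/dL (Section 5.5.2). Marked abnormalities in those analytes should therefore mostly be absent at baseline, although PCS thresholds are not stated. A value taken just before daily dosing is also a defensible reference for the effect of the daily regimen, and Section 8 defers further analysis of the flare-up regimen to the SAP, which is not shown. Finally, Section 8.8 lists all safety data, so nothing is lost from the record. What stands is that SAS-based tables would omit exposed subjects, and that the baseline is not drug-free for some children.

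**Conclusion.** The PVO-1A-204 SAS definition contradicts its own section and the start of daily dosing under Amendment 3, and it should be corrected. Its effect lies between none and a material share of a set of about nine: 11% per omitted subject, with k unknown. The PVO-1A-202 gap is confined to subjects exposed only in Part A, on the 10/5 mg regimen, whom Part D may bring back; their number is not given either.

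The baseline point is secondary. It concerns change-from-baseline and new-onset PCS summaries, and it reaches growth measures only if height and knee height are treated as other continuous safety parameters, which Section 8.8.3 does not say. The definitions show that exposed subjects could be omitted. They do not show that any were, or that a particular harm is understated. Severity: SHOULD-FIX.

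**What to change.** In Section 8.3 of both protocols, or in the SAP with the deviation recorded, define the SAS as all enrolled subjects with at least one palovarotene dose in the study under any part or amendment, and summarise safety by part and regimen. The PAS then follows as a subset, and Part A-only subjects seen in Part D have a denominator.

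In Section 8.8.3, keep the value before non-flare-up dosing as the baseline for the daily-regimen summary. Add a second, labelled baseline: the last value before the first palovarotene dose in this study, with Study 201 exposure flagged. Use it for additional change and new-onset PCS summaries. State that subjects treated only for flare-ups use this second baseline, and say whether height and knee height fall under the rule.

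The cost is about two sentences in Section 8.3 and one or two in Section 8.8.3 of each protocol, a re-derived population flag and a second baseline flag. Some first-dose values will be old or missing and should be reported as such. In growing children, change from an older value mixes growth with any drug effect, so the two baselines should be shown side by side.
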